Specific Aim 2: Brain Changes - We aim to determine if white matter fiber tracts show improved integrity as measured by diffusion imaging (DKI) before, after a 2-week treatment taVNS-paired feeding course, and whether treatment improves neuronal energetics in the basal ganglia as measured by magnetic resonance spectroscopy (MRS). Unsedated MRS and DKI imaging will last approximately 40 minutes, and will be done before and after the two-week taVNS-paired rehab treatment session. The changes in white matter tract diffusion parameters and N-acetylaspartate (NAA) and glutathione (GSH) concentration in the basal ganglia and thalamus will be compared with published changes of these parameters over gestational age in preterm infants (14, 15) and with our own MRS data in preterm and HIE infants who did not receive taVNS.

We will perform DKI to determine the effects of taVNS on plasticity, and to identify areas of the brain involved in afferent vagal activation. We propose utilizing the concurrent taVNS/fMRI method developed by [name] at MUSC to determine whether taVNS activates the CNS and afferent vagal network in a subset of preterm and term infants in the study.

B. BACKGROUND AND SIGNIFICANCE

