[name], Ph.D, obtained his doctorate under [name], and has extensive experience and background in clinical TMS and taVNS, especially in the development of novel protocols for neurological disorders. His thesis work involves systematic elucidation of the dose response of taVNS on heart rate, use of heart rate as a biomarker of taVNS effect, and the use of taVNS with fMRI in determining pathways and regions affected by taVNS in adults. He determined that the 'on' pulse heart rate change was a mean of -3 beats per minute (bpm) while the 'off' pulse heart rate change was +6 bpm. Although these are statistically significant and measurable changes, they are physiologically insignificant. Nevertheless, this will be an important biomarker for infants, but is not expected to result in safety concerns. [name] careful and thorough studies lay the safety and efficacy groundwork for the current proposal.

D. RESEARCH DESIGN AND METHODS (including data analysis)

Due to the novelty of these studies, [name] will be present for each taVNS-paired feeding session conducted in the first participants, and as needed thereafter. [name] and or [name] will monitor taVNS effects. If any adverse events are noticed which are not described in the consent or are serious, we will inform the IRB before continuing with the next enrolled subject. Importantly, all of these methods have been done before, and published by our and other groups in adults, and we believe these extra precautions will assure the safety and well-being of any participants enrolled.

taVNS-paired feeding to enhance feeding behavior in neonates

Screening

Prospective participants will be identified by the PI ([name]) at the MUSC neonatal intensive care units (Level II and III), and checked for potential inclusion (please see the uploaded taVNS screening form). [name], and other clinical OTs based in the nursery may also mention the study to parents and refer them to [name] if they are interested in participating.

Participants

Inclusion criteria:

Infants must be clinically stable, on minimal respiratory support (nasal cannula, or room air), in discussions about Gtube placement for poor po feeding and are currently greater than or equal to 39 weeks post-menstrual age and

- 1) If born premature have been working on oral feeding for 30days;
or

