- 2) If term Infant with significant medical issues that have precluded oral feeding, such as hypoxic ischemic encephalopathy (HIE), have been working on oral feeding for 14days.

Exclusion criteria:

- 1) Unstable infants or those requiring respiratory support involving positive pressure.
- 2) Major unrepaired congenital anomalies
- 3) Anomalies/conditions that limit feeding volumes
- 4) Cardiomyopathy
- 5) Repeated episodes of autonomic instability (apnea or bradycardia) which are not self-resolving *

*Preterm infants commonly have short periods of shallow or absent breathing or lower heart rate termed apnea and bradycardia, respectively, and most are being treated for these physiologic manifestations of prematurity with caffeine, an effective central stimulant. Infants are on cardiorespiratory monitors through the nursery stay to capture events, many of which are self-resolving. Infants who require repeated episodes of tactile stimulation to come out of these events are defined as *unstable*.

Neonates who are beginning oral feeds after medical treatment for critical illnesses, such as HIE brain injury, will be included as these neonates represent a population in which taVNS-paired feeding could present the largest success in overcoming impaired brain development. Congenital syndromes may be included if the infants do not have major, unrepaired anomalies or anomalies that limit feeding volumes.

Written informed consent will be obtained from the mother if available and if she has custody or decision making authority for the participant, otherwise a parent or legal guardian, prior to participation in the experimental paradigm. Department of Social services may have custody of infant but require the parent or foster parent to consent for all medical procedures.

Electronic Consent will be used for situations when the parent (or Legally Authorized Representative) is at another hospital and cannot travel to MUSC to provide consent in person. We will use the approved REDcap system to obtain consent. [name] or other approved study personnel will go over the entire consent document on the phone with the parent to ensure comprehension and to confirm identity. Parent will be given a copy of the completed, signed consent form in person or by email or fax.

Study Design

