1. RISKS TO THE SUBJECTS

The human subjects involved in this research will be preterm neonates or infants with critical illnesses that preclude oral feeding, such as HIE. Inclusion criteria involves 2 main groups. The first is comprised of typical pre-term, high risk neonates who are in the convalescent near and post-term period and learning to po feed. The second is comprised of neonates that present after severe medical illnesses or brain injury. In both cases, the infants can only be enrolled if they are stable, not making progress with OT training, and are in discussion for Gtube placement. Participants will be excluded if they have major unrepairs congenital abnormalities that limit volume of feeds, cardiomyopathy, significant autonomic instability, such as repetitive, unresolved bradycardia or apnea, or use a continuous positive airway pressure (CPAP) device or other form of high respiratory support preventing them from breathing without assistance.

Targeted/Planned Enrollment Table

Total Planned Enrollment: 40 babies (active)

TARGETED/PLANNED ENROLLMENT: Number of Subjects receiving active taVNS			
Ethnic Category	Sex/Gender		
	Females	Males	Total
Hispanic or Latino	4	5	9
Not Hispanic or Latino	15	16	31
Ethnic Category: Total of All Subjects*			

Racial Categories			
American Indian/Alaska Native			
Asian			
Native Hawaiian or Other Pacific Islander			
Black or African American	8	7	15
White	12	13	25
Racial Categories: Total of All Subjects*	20	20	40

*The “Ethnic Category: Total of All Subjects” must be equal to the “Racial Categories: Total of All Subjects”.

Volunteers of all ethnicities and racial categories will be accepted into this study protocol. No preference will be given based on race, gender or ethnicity. No vulnerable populations or special classes of subjects will be considered for participation.

b. Sources of Materials

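### Aim 2's MRS references are not stated to match trial infants on eligibility, scan age or scan interval, so a difference in NAA or GSH change cannot be attributed to taVNS

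*Combined protocol and SAP*

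**What the plan says.** Section A, Specific Aim 2 sets out to learn whether treatment improves neuronal energetics in the basal ganglia, measured by MRS. Scans "will be done before and after the two-week taVNS-paired rehab treatment session". The changes in NAA and GSH are then set against two references. One is "published changes of these parameters over gestational age in preterm infants". The other is a comparison "with our own MRS data in preterm and HIE infants who did not receive taVNS".

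Section D, Participants, defines the treated infants far more narrowly. They must be "in discussions about Gtube placement for poor po feeding and are currently greater than or equal to 39 weeks post-menstrual age". In addition, the preterm group must meet the condition "If born premature have been working on oral feeding for 30days", and term infants with significant medical issues such as HIE must "have been working on oral feeding for 14days". Section E.1 repeats the restriction: "the infants can only be enrolled if they are stable, not making progress with OT training, and are in discussion for Gtube placement".

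Study Design gives active stimulation to every consented infant. For imaging, Data Analysis names only t-tests on kurtosis parameters: paired for pre versus post, and unpaired for full oral feeders versus infants needing a G-tube.

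**The concern.** With no untreated arm, a rise in NAA or GSH over the course could simply be maturation, so the outside references have to carry the treatment question. They can do that only if untreated infants like those in the trial, scanned at similar ages and over a similar interval, would have changed as the reference infants did. The plan neither states this nor arranges for it.

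The protocol itself gives two reasons why it matters. Aim 2 treats these parameters as changing over gestational age, so age at scan and time between scans affect the expected change. The introduction to Section A says that HIE interrupts development of the cortex and basal ganglia and, depending on severity, contributes to the inability to feed. Selecting infants because they fail to feed may therefore also select on injury in the region being measured.

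At stake is the mechanistic claim of Aim 2, which could be carried forward into the larger randomized trial that the Limitations paragraph has in view. The bias could run either way. Slower maturation in persistent poor feeders would hide a benefit, and a reference scanned where the age curve is flatter would create one.

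**Working it through.** The plan states no sample size, power, effect size or standard deviation for the MRS comparison, so there is no figure to reproduce. The check sets the definitions side by side.

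| Feature | Trial infants | Published reference | In-house reference |
|---|---|---|---|
| Birth group | Preterm, or term with illness such as HIE | Described as preterm | Preterm and HIE |
| Age at first scan | At least 39 weeks (follows from entry) | Framed over gestational age | Not stated |
| Scan interval | Around a two-week course in Aim 2; Study Design allows 2 to 3 weeks of treatment | Not stated | Not stated; nor whether scans were serial |
| Feeding failure, G-tube discussion | Required | Not stated | Not stated |
| Number of infants | Up to 40 | Not stated | Not stated |

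**Does comparing change rather than level solve it?** Write each infant's change as baseline-free growth: change = (rate of maturation or recovery) × (weeks between scans) + (taVNS effect, if treated). Stable baseline differences cancel. The difference in mean change between treated and reference infants is then

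taVNS effect + [expected untreated change in trial infants − expected change in reference infants].

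The bracket is zero only if rate and interval agree in the two groups. Rate may depend on age, diagnosis and severity. Nothing planned makes the bracket zero or estimates it.

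**Does anything elsewhere in the plan fill the gap?** Data Analysis has no NAA or GSH test and no covariates. The once-versus-twice-daily comparison is planned for feeding success, not MRS. The historical group in Study Design was selected on feeding failure and gastrostomy, but is not described as having MRS data.

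**Illustration only, all inputs assumed.** Suppose taVNS has no effect, the bracket equals b standard deviations of change, there are n infants per group, and a two-sided 5% test is used (the plan specifies none). The chance of a significant difference in the direction of the bias is Φ(b√(n/2) − 1.96).

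| n per group | b = 0 | b = 0.25 | b = 0.5 | b = 0.75 | Detectable with 80% power: (1.96 + 0.84)√(2/n) |
|---|---|---|---|---|---|
| 10 | 2.5% | 8% | 20% | 39% | 1.25 SD |
| 20 | 2.5% | 12% | 35% | 66% | 0.89 SD |
| 40 | 2.5% | 20% | 61% | 92% | 0.63 SD |

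For example, n = 40 and b = 0.5 give 0.5 × √20 − 1.96 = 0.28, and Φ(0.28) = 61%. The table shows what a bias of a given size would do. It does not show that such a bias exists.

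**The case against.** The strongest reply is that silence is not a demonstrated difference. Aim 2 is a one-sentence summary. Part of Section C, Preliminary Studies, was not in the text available for review, and an in-house MRS cohort might be described there. This stands: the point concerns what the available plan states, not what the comparator infants are known to be.

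Age is also partly handled. The published comparison is of changes over gestational age, which allows a reference at a similar age to be read off. That helps for this one source, but not with feeding failure or G-tube selection, and no age alignment is stated for the in-house data. The preterm wording of the published reference should not be pressed far as a gap for HIE infants, because the in-house group includes them and one cited paper is titled as concerning neonatal brain injury.

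Imaging is a secondary purpose of an open-label pilot, safety and feasibility come first, and the missing sham arm is already acknowledged. All true, and this limits the point to Aim 2. The acknowledged limitation does not cover it, though, because Aim 2 still asks a treatment-effect question of these references.

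Finally, enough untreated infants who meet every criterion and have two scans may not exist. That is a fair doubt, and it is why the fix needs a fallback.

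**Conclusion.** The point holds as a limit on what Aim 2's MRS comparison can show. Followed as written, the plan cannot separate a taVNS effect on NAA or GSH from maturation, injury severity or selection on feeding failure. Neither direction nor size of any bias can be determined, because the documents give no metabolite values, comparator numbers or comparator scan ages.

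A reader might go further and infer that selection and timing account for as much of any difference as taVNS does. The documents do not support that, since it is a quantitative statement with no figures behind it. Nor do they show that the reference groups actually differ from trial infants, or that their scan intervals differ by any particular amount.

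The conclusion assumes that no eligibility, timing or adjustment rule for the MRS references appears in the missing part of Section C. It does not touch the feeding outcomes or the safety assessment. The change should be made, but the trial does not depend on it.

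**What to change.** 1. In Aim 2 and Data Analysis, define the in-house comparator as untreated infants with two MRS scans. Report their number, post-menstrual age at each scan, scan interval and birth group.
2. For each infant compute (second value − first value) / weeks between scans, for NAA and for GSH. Compare treated with untreated infants in a linear model with post-menstrual age at first scan and birth group (preterm or term/HIE) as covariates.
3. Limit the primary comparison to in-house infants who met the Section D inclusion criteria at their first scan, where enough exist. Fix in advance what counts as enough.
4. Use the published gestational-age data as descriptive context only.
5. If too few in-house infants qualify, or serial scans are lacking, reword Aim 2 to say that the MRS results are descriptive and do not show a treatment effect.

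This takes a chart check of the existing MRS infants and a few sentences of text. The price is a smaller comparator group, with less precision, and a more modest Aim 2 claim. Even with these steps the comparison stays non-randomized, and unmeasured differences in injury severity may remain.

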[name], Ph.D, obtained his doctorate under [name], and has extensive experience and background in clinical TMS and taVNS, especially in the development of novel protocols for neurological disorders. His thesis work involves systematic elucidation of the dose response of taVNS on heart rate, use of heart rate as a biomarker of taVNS effect, and the use of taVNS with fMRI in determining pathways and regions affected by taVNS in adults. He determined that the 'on' pulse heart rate change was a mean of -3 beats per minute (bpm) while the 'off' pulse heart rate change was +6 bpm. Although these are statistically significant and measurable changes, they are physiologically insignificant. Nevertheless, this will be an important biomarker for infants, but is not expected to result in safety concerns. [name] careful and thorough studies lay the safety and efficacy groundwork for the current proposal.

D. RESEARCH DESIGN AND METHODS (including data analysis)

Due to the novelty of these studies, [name] will be present for each taVNS-paired feeding session conducted in the first participants, and as needed thereafter. [name] and or [name] will monitor taVNS effects. If any adverse events are noticed which are not described in the consent or are serious, we will inform the IRB before continuing with the next enrolled subject. Importantly, all of these methods have been done before, and published by our and other groups in adults, and we believe these extra precautions will assure the safety and well-being of any participants enrolled.

taVNS-paired feeding to enhance feeding behavior in neonates

Screening

Prospective participants will be identified by the PI ([name]) at the MUSC neonatal intensive care units (Level II and III), and checked for potential inclusion (please see the uploaded taVNS screening form). [name], and other clinical OTs based in the nursery may also mention the study to parents and refer them to [name] if they are interested in participating.

Participants

Inclusion criteria:

Infants must be clinically stable, on minimal respiratory support (nasal cannula, or room air), in discussions about Gtube placement for poor po feeding and are currently greater than or equal to 39 weeks post-menstrual age and

- 1) If born premature have been working on oral feeding for 30days;
or
- 2) If term Infant with significant medical issues that have precluded oral feeding, such as hypoxic ischemic encephalopathy (HIE), have been working on oral feeding for 14days.

Exclusion criteria:

- 1) Unstable infants or those requiring respiratory support involving positive pressure.
- 2) Major unrepaired congenital anomalies
- 3) Anomalies/conditions that limit feeding volumes
- 4) Cardiomyopathy
- 5) Repeated episodes of autonomic instability (apnea or bradycardia) which are not self-resolving *

*Preterm infants commonly have short periods of shallow or absent breathing or lower heart rate termed apnea and bradycardia, respectively, and most are being treated for these physiologic manifestations of prematurity with caffeine, an effective central stimulant. Infants are on cardiorespiratory monitors through the nursery stay to capture events, many of which are self-resolving. Infants who require repeated episodes of tactile stimulation to come out of these events are defined as *unstable*.

Neonates who are beginning oral feeds after medical treatment for critical illnesses, such as HIE brain injury, will be included as these neonates represent a population in which taVNS-paired feeding could present the largest success in overcoming impaired brain development. Congenital syndromes may be included if the infants do not have major, unrepaired anomalies or anomalies that limit feeding volumes.

Written informed consent will be obtained from the mother if available and if she has custody or decision making authority for the participant, otherwise a parent or legal guardian, prior to participation in the experimental paradigm. Department of Social services may have custody of infant but require the parent or foster parent to consent for all medical procedures.

Electronic Consent will be used for situations when the parent (or Legally Authorized Representative) is at another hospital and cannot travel to MUSC to provide consent in person. We will use the approved REDcap system to obtain consent. [name] or other approved study personnel will go over the entire consent document on the phone with the parent to ensure comprehension and to confirm identity. Parent will be given a copy of the completed, signed consent form in person or by email or fax.

Study Design

Up to 40 preterm/HIE neonates will be enrolled in this prospective, open-label safety and feasibility trial, with a dose response. The experimental paradigm consists of 2 to 3 weeks of once or twice daily taVNS-paired feeding.

Our control group was investigated by Drs. [name] and [name] at MUSC, who have researched all infants failing feeding and getting Gastrostomy tubes in our nurseries over the past 5 years. We can compare our data to this historical group at our own institution.

All consented participants will receive the active stimulation condition.

taVNS Stimulation (in Detail)

After obtaining consent and describing this procedure to the parents and all members of the baby's care team, we will first, with a 500 μ s, 25Hz pulse, gradually increase the intensity of the TENS unit until the baby can first feel something in their ear. We will use the facial expression change and fidgety movements to determine when the infants feel the stimulation. This intensity will be recorded as the perceptual sensory threshold. The stimulation intensity we will use for this study on taVNS-paired feeding is a small decrement from the perceptual sensory threshold for each infant (-0.1mA), a point at which they should not react to the stimulation. We will retest the sensory threshold before every session.

Determination of Perceptual Threshold

1. Electrode clip will be placed on the left tragus in an enrolled infant at rest. Starting at 0.2mA at 25Hz, we will deliver 5 seconds of pulses, and increase by 0.1mA until the perceptual threshold is achieved by observation of the infant's facial expression, fidgety movements, or NIPPS score. This will be termed the perceptual threshold.
2. We will then deliver this level of microcurrent while the infant is feeding on the first day to determine if the perceptual threshold changes with feeding. Current will then be held constant while pulse width and frequency will be set at 500us and 25Hz, respectively.

3. Finally, we will decrease the microcurrent by 0.1mA *below the perceptual threshold* and administer this taVNS treatment during the feeding and deliver this only while the infant is actively sucking from the bottle.
4. The total duration of this 'on-and-off' taVNS stimulation treatment will continue for 30 minutes or the duration of the feed.
5. We may manually trigger the taVNS stimulation or place a gel EMG electrode over the temporomandibular joint area to trigger the taVNS impulse.

Once the daily taVNS intensity has been determined, the treatment will continue to be administered in conjunction with the daily OT feeding once or twice daily.

As the baby begins to suck from the bottle or breast, stimulation will be triggered and a timer will be started. Sometimes the infant has non-nutritive sucking and it is difficult for the operator to discern between these lip motions and real suck/swallow. We wish to stimulate during sucking motions that include swallowing but may occasionally pair with ineffective and incomplete lip sucking, characteristic of more immature patterns. We may use manual triggering by a research assistant or triggering by the EMG at the buccinator muscle to ensure accurate delivery of impulses and pairing of impulse with sucking/swallowing.

The stimulation will continue until the baby stops sucking, at which point the stimulation will be stopped and the timer will stop, until the baby begins to suck again. The typical feeding OT session lasts up to 30 minutes. Physiological data will be monitored continuously as measured by the echocardiogram (ECG). Neonatal Infant Pain Scale (NIPS) data will be collected at beginning, middle and the end of treatment session. The NIPS rating scale currently in use in the nursery is included in this submission. These studies will be conducted in both level II and III Neonatal Intensive Care Units (NICUs), depending on the location and of the enrolled participants.

taVNS Device

taVNS will be delivered to the left ear only using an active (tragus) location for the taVNS clip using either the Digitimer Type DS7AH (Digitimer Ltd, Hertfordshire, England) or Soterix 0125-LTE stimulator customized for our infant trials. Both are TENS units and are cleared by the FDA for electrical nerve stimulation in research trials (See uploaded documents from Soterix). We also recently received FDA Breakthrough device designation for our BabySTrong taVNS infant feeding system, based on a customized 0125-LTE Soterix taVNS unit. TENS units are widely used in children with overactive bladder and dysfunctional voiding and stooling (44-45) and for analgesia in children, and as a treatment for chronic pain, including cancer (46). A custom electrode, embedded within a carbon matrix will be used to stimulate the auricular branch of the vagal nerve at the tragus. We will then trigger the taVNS unit to deliver the microcurrent or to stop the microcurrent when the infant is actively sucking and swallowing.

Safety Monitoring

Prior to determination of the daily sensory threshold of the infant, an initial pain level will be recorded using the NIPS. Previous studies using pain as a marker for safety in neonates check for pain halfway through the respective treatment (39-40). TENS treatments in studies examined in creating our protocol

typically lasted 30 minutes (41-43). Because the duration of the taVNS-paired feeding varies daily and will ultimately exceed 10 minutes, we will record pain levels before, at the end of treatment, and additionally at 5 and 10 minutes for longer sessions. This is shown in more detail in the *In Session Form* included.

In an effort to standardize delivery of taVNS-paired feeding treatment, the taVNS device will be placed in the left ear as default. Skin redness at the site of taVNS attachment to the ear is possible after treatment, but is expected to be transient. In order to prevent injury to the skin in contact with the device, each day the left ear will be first examined for redness prior to attaching the taVNS device. However, if there is skin redness at the site attachment to the ear prior to each day's treatment, we will switch the stimulation that day to the right ear. If these symptoms are persistent, we will decrease the stimulation.

ECG will be monitored during each treatment session. The HR measures will provide valuable data for safety analysis as well as immediate markers for physiological safety during taVNS-paired feeding. Bradycardia will be defined by NICU standards of <80bpm for 5 seconds.

In all sessions of taVNS-paired feeding, [name] or research staff trained in taVNS will be present. At any point during taVNS-paired feeding, the research staff will decrease stimulation intensity, if they feel the participant is in mild distress.

Developmental follow-up

Developmental follow-up is routine in all preterm and HIE infants, with clinical visits occurring every 3 months at Neonatal High-risk clinic. If parents do not bring their infants back for standard of care developmental testing, and if more convenient for parents, the developmental testing will be performed by Drs. [name] and/or [name] in the home or other location of the parent's choosing. Developmental testing in the home will be free of charge, and test information will be discussed with parents during the testing session and then uploaded into EPIC for other care providers.

Payment

No payment will be provided in this trial.

Data Analysis

For safety we will compare HR changes from baseline to during taVNS within subjects. We will compare treatment before and after the taVNS-paired feeding treatment for the rate of feeding volume increase, and days to full po feeds. We will use repeated measures ANOVA to analyze repeated measures such as HR over 5 minutes and mean daily feeding volumes in 7-10 day epochs. We will analyze the number of infants who reach full feeds vs requiring G-tube during taVNS-paired feeding, between once and twice daily stimulation by Chi-squared. We will assess differences in kurtosis parameters from pre-to post taVNS scans by paired t-test, and between those that reach full oral feeds vs those that require a Gtube by unpaired t-test.

Estimated Difficulties, Limitations and Time Frames

Estimated Difficulties. Many of the initial parameters for taVNS in humans, such as frequency and pulse width, were accomplished in trials at MUSC by [name] et al. that were approved by the IRB. In one sense, we will be shrinking many of the components into miniature form to deliver stimulation to neonates and infants. In spite of the clear differences in size and skin between the neonatal and adult ear, the custom electrodes have been fitted to several different weights of infants (2.5-4.0 kg).

Limitations. We will not be delivering a SHAM stimulation paradigm (electrodes and Digitizer with appearance of taVNs treatment without actual current). Our goal is to determine safety and feasibility of active treatment with a dose response in order to investigate whether this should be administered in a larger randomized control trial. In this respect, the comparison we lose in not having a SHAM stimulation is offset by the validation we will receive in the safety and feasibility of active treatment. We will compare our overall results with characteristics of infants who required a Gtube from [name] and [name]'s publications.

Estimated Time Frames. The duration of the study will likely be ~4 years, with 2 years of active enrollment and 18 months of follow-up.

E. PROTECTION OF HUMAN SUBJECTS

